10.1. DERIVATIONS

- Age (years) = Date of Signature of Informed Consent – Date of Birth

Notably, due to privacy law applicable in some countries included in this Study (e.g. Italy), in the electronic CRF only the months and the year of birth were collected. Therefore, since the day of birth was not collected on electronic CRF, this will be defined as the first day of the month of birth.

- Time form Diagnosis (months) = Date of Signature of Informed Consent - Date of Initial Diagnosis

11. MEDICAL HISTORY

Medical History information will be presented for the SAF analysis set.

- Medical History will be coded using version 20.1 of Medical Dictionary for Regulatory Activities (MedDRA) dictionary.
- Medical History conditions are defined as those conditions recorded on eCRF form “MH”.
- Presented by System Organ Class (SOC) and Preferred term (PT).

Document: PPD

Author: PPD

Version Number:

V2.2

Version Date:

21 March 2018

Template No: CS_TP_BS016 – Revision 3

Reference: CS_WI_BS005

Effective Date: 01May2012

Copyright © 2012 Quintiles Transnational Corp. All rights reserved.

The contents of this document are confidential and proprietary to Quintiles Transnational Corp. Unauthorized use, disclosure or reproduction is strictly prohibited.

12. PRIOR AND CONCOMITANT ILLNESSES

Prior and Concomitant Illnesses will be presented for the SAF analysis set.

- Prior and Concomitant Illnesses will be coded using the version 20.1 of MedDRA dictionary.
- Prior disease medications are defined as those starting and ending prior to the first administration of investigational study drug.
- Concomitant Illnesses are conditions recorded on eCRF form “MH” and which started prior to or at Screening and are ongoing at the date of Screening.
- Presented by SOC and PT.

12.1. POST-TREATMENT DISEASES

Post-treatment disease will be presented for the SAF analysis set.

- Post-treatment diseases will be coded using the version 20.1 of MedDRA Dictionary.
- Post-treatment diseases are conditions recorded on electronic CRF in the Form “AE” and which started after the last Study drug intake.
- Presented by SOC and PT.

13. MEDICATIONS (I.E. DRUGS)

Prior medications to treat PV will include regimens discontinued up to 24 weeks prior to enrolment. The information captured in electronic CRF included drug name, start and stop dates, best response to therapy (*where applicable*) and reason for discontinuations.

Medications will be presented for the SAF analysis set and coded using the 01SEP2017 version of WHO-DRL Dictionary. Frequency tabulations will be presented for prior and concomitant medication by primary therapeutic subgroup (3rd level ATC code), generic name and active principle.

See [Appendix 2](#) for handling of partial dates for medications, in the case where it is not possible to define a medication as prior, concomitant, or post treatment, the medication will be classified by the worst case (i.e. concomitant medication):

- ‘Prior’ drug medications are defined as those starting and ending prior to the first administration of investigational Study drug (i.e. C1D1).

Document: PPD

Author: PPD

Version Number:

V2.2

Version Date:

21 March 2018

Template No: CS_TP_BS016 – Revision 3

Reference: CS_WI_BS005

Effective Date: 01May2012

Copyright © 2012 Quintiles Transnational Corp. All rights reserved.

The contents of this document are confidential and proprietary to Quintiles Transnational Corp. Unauthorized use, disclosure or reproduction is strictly prohibited.

- 'Concomitant' drug medications are defined as those started at or after first administration of Study drug (i.e. C1D1) and include those started prior to the first administration of investigational Study drug (i.e. C1D1) but continued during the Study.
- 'Post' drug medications are defined as drug medications which started after the last Study drug intake.

13.1. NON-DRUGS THERAPIES

Prior and significant non-drug therapies (e.g. phlebotomies, transfusions) to treat PV will include regimens discontinued up to 24 weeks prior to enrolment. Non-drug-therapies will be summarised by type of procedure (i.e. transfusion, phlebotomy, other), date of procedure, reason for procedure. Non-drug therapies (e.g. transfusion, phlebotomy) will be presented for the SAF analysis set.

See [Appendix 2](#) for handling of partial dates for non-drugs therapies, in the case where it is not possible to define a non-drug therapy as prior, concomitant, or post treatment, the non-drug therapy will be classified by the worst case (i.e. concomitant non-drug therapy):

- 'Prior' non-drug therapies are defined as those starting and ending prior to the first administration of investigational Study drug (i.e. C1D1).
- 'Concomitant' non-drug therapies are defined as those started at or after first administration of Study drug (i.e. C1D1) and include those started prior to the first administration of investigational Study drug (i.e. C1D1) but continued during the Study.
- 'Post' non-drug therapies are non-drug therapies which started after the last Study drug intake.

Frequency tabulations will be also presented for significant non-drug therapies.

Notably, all phlebotomies performed in the first 3 weeks of treatment will be not counted to assess the clinico-haematological response according to the clinico-haematological ELN response criteria [\[1\]](#) at C3D28 and at C3D28 in **Parts A** and **B**.

14. STUDY MEDICATION EXPOSURE

Exposure to study medication in days will be presented for the SAF analysis set.

The date of the first investigational study drug of each patient will be taken from the

"On-site Dosing (DOSING)" raw data panel. This date of first investigational study drug administration

Document PPD

Author: PPD

Version Number:

V2.2

Version Date:

21 March 2018

Template No: CS_TP_BS016 – Revision 3

Reference: CS_WI_BS005

Effective Date: 01May2012

Copyright © 2012 Quintiles Transnational Corp. All rights reserved.

The contents of this document are confidential and proprietary to Quintiles Transnational Corp. Unauthorized use, disclosure or reproduction is strictly prohibited.

(Day 1) is the key variable RFSTDTN and used in the calculation of relative days.

The date of first study medication administration will be taken from the eCRF “Dosing” Form (C1D1).

The date of the last investigational study drug of each patient will be taken from the “Patient Disposition” form of eCRF. If the date is missing, the date of the last visit will be imputed, if appropriate. This date of last investigational study drug is the key variable RFENDTN.

The duration (days) of exposure and the daily dosage (mg) of Givinostat will be calculated for each patient, and will be summarized descriptively including the mean, standard deviation, median, minimum and maximum.

A listing of treatment exposure data, including the first and last dates of Study drug administration will be presented by-subject and within-subject by available interval and overall exposure.

Interruptions, compliance, and dose changes are not taken into account for duration of exposure.

Reason for treatment discontinuation and number of patients treated beyond protocol-specified discontinuation criteria will also be summarised. Analysis will be based on safety population.

In general, In the case of missing data on the eCRF, the cycle C1D1 visit date and the last visit cycle performed date will be used in order to determine the first and last date of study medication.

14.1. DERIVATIONS

The duration of investigational study drug or exposure to treatment is equal to the day number of the last day of drug administration (LDA) and is derived as follows from the previous two dates (RFSTDTN and RFENDTN):

$$\text{LDA (days)} = (\text{Date of Last Drug Administration [RFENDTN]} - \text{Date of First Drug Administration [RFSTDTN]}) + 1$$

LDA then indicates the relative day that the last dose of investigational study drug is administered per patient, as calculated relative to the first day of dosing.

Document: PPD

Author: PPD

Version Number:

V2.2

Version Date:

21 March 2018

Template No: CS_TP_BS016 – Revision 3

Reference: CS_WI_BS005

Effective Date: 01May2012

Copyright © 2012 Quintiles Transnational Corp. All rights reserved.

The contents of this document are confidential and proprietary to Quintiles Transnational Corp. Unauthorized use, disclosure or reproduction is strictly prohibited.

15. STUDY MEDICATION COMPLIANCE

The Investigator recorded in the electronic CRF the assigned dose of Givinostat and any dose reduction (*if applicable*) to allow the evaluation of compliance to treatment. At each visit, patients brought back to the Study site all drug bottles previously received (i.e. used, partially used and unused) and receive a new Study drug supply. The number of residual capsules in the dispensed bottles were counted by the Investigator and reported in the electronic CRF.

Compliance with Givinostat treatment will be calculated based on the Study drug accountability documented by the site staff and monitored by Italfarmaco S.p.A. or its designee (i.e. capsule counts).

A patient will be considered sufficiently compliant with Givinostat treatment if he/she has taken at least 80% of the prescribed dose over the total duration of Study drug dosing. In addition, patients who didn't experience a DLT and missed more than 10% of the doses in Cycle 1 of **Part A** will be considered not sufficiently compliant.

Treatment compliance to Study drug will be presented for the SAF analysis set, ITT analysis set, PP analysis set, MTD analysis set and PK analysis set, during all six Cycles of treatment (i.e. from C1D1 to C6D28). Treatment compliance will be calculated for C1D1 – C1D28 in **Part A**, and C1D1 – C6D28 in **Parts A and B** (both Stages).

Treatment compliance per interval is defined as the number of capsules that were actually taken within a given interval relative to the number of capsules that should have been taken by the patient for the duration of actual treatment exposure for that interval.

Summary statistics for the Actual Total Dose delivered (mg), Givinostat Dose Intensity (mg/day) will be presented.

Summaries showing Givinostat dose modification during the Study will be presented by treatment group.

15.1. DERIVATIONS

In general, the percentage compliance (%), assessed by capsule count, will be calculated as follows:

Document: PPD

Author: PPD

Version Number:

V2.2

Version Date:

21 March 2018

Template No: CS_TP_BS016 – Revision 3

Reference: CS_WI_BS005

Effective Date: 01May2012

Copyright © 2012 Quintiles Transnational Corp. All rights reserved.

The contents of this document are confidential and proprietary to Quintiles Transnational Corp. Unauthorized use, disclosure or reproduction is strictly prohibited.

- “Per visit” Compliance to study medication will be calculated as follows:

$$\frac{\{([N \text{ of Capsules dispensed at Visit } (n)] - [N \text{ of Capsules returned at Visit } (n+1)])\}}{[[\text{Date of Visit } (n+1)] - [\text{Date of Visit } (n)]] \times \text{Number of capsules prescribed by day}} \times 100$$

- Overall Compliance to study medication will be calculated as follows:

$$\frac{\{([N \text{ of Capsules dispensed at Cycle 1}] - [N \text{ of Capsules returned at Cycle 2}]) + \dots + ([N \text{ of Capsules dispensed at Cycle}(n-1)] - [N \text{ of Capsules returned at Cycle}(n)])\}}{[[\text{Date of Cycle}(n)] - [\text{Date of Dispensing at Cycle 1}]+1] \times \text{Number of capsules prescribed by day}} \times 100$$

Also for the last cycle compliance calculation this formula will be used as the last dose of study drug date considering from disposition page.

For patients who permanently stop the study medication, the “Date of visit (n)” will be replaced by the date of study withdrawal.

A patient will be considered sufficiently compliant with Givinostat treatment if he/she has taken at least 80% of the prescribed dose over the total duration of study drug dosing.

The calculated percentage compliance per interval will be categorized as:

A) **Part A** – Cycle 1:

- Too Low: ≤ 90% compliance.
- Adequate: > 90% to ≤ 100% compliance.
- Too High: > 100% compliance.

B) **Part A** (all Cycles) and **Part B:**

- Too Low: < 80% compliance.
- Adequate: ≥ 80% to ≤ 100% compliance.
- Too High: > 100% compliance.

Document: PPD

Author: PPD

Version Number:

V2.2

Version Date:

21 March 2018

Template No: CS_TP_BS016 – Revision 3

Reference: CS_WI_BS005

Effective Date: 01May2012

Copyright © 2012 Quintiles Transnational Corp. All rights reserved.

The contents of this document are confidential and proprietary to Quintiles Transnational Corp. Unauthorized use, disclosure or reproduction is strictly prohibited.

Categories of overall compliance will be presented by treatment group using default summary statistics. Calculated compliance (%) per applicable interval and overall will be also presented.

All drug accountability data will be presented, that is, the number of capsules dispensed and returned at each applicable interval. The total number of capsules taken per applicable interval and overall (%), as well as the calculated compliance (%) per applicable interval and overall will be presented, *if applicable*.

The Givinostat summary statistics for the Actual Total Dose delivered (mg) and Dose Intensity Givinostat: DI (mg/day) will be presented and calculated as follow:

Actual Total Dose delivered (mg) = sum over all days of actual dose received (mg).

Dose Intensity Givinostat: DI (mg/day) = [Actual Total Dose Level of Givinostat (mg)/Duration of exposure (days)].

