V2.1	PPD	SAP section 19.1: Additional analysis of patients without the symptom of headache, pruritus and microvascular symptoms (i.e MPN SAF Score =0) and number and percentage of patient with symptom score from 0 to 3, from 4 to 6 and more than 7 are added. Also patients rate with normalized WBCs (WBCs count ≤ 10 x 10 ⁹ /L), Patients rate with normalized platelets (platelets ≤ 400 x 10 ⁹ /L) and Patients rate with normalized haematocrit (haematocrit <45% without phlebotomy) are added. The following tables/figures are added.

Document: PPD

Author: PPD

Version Number:

V2.2

Version Date:

21 March 2018

Template No: CS_TP_BS016 – Revision 3

Reference: CS_WI_BS005

Effective Date: 01May2012

Copyright © 2012 Quintiles Transnational Corp. All rights reserved.

The contents of this document are confidential and proprietary to Quintiles Transnational Corp. Unauthorized use, disclosure or reproduction is strictly prohibited.

		
Tables 14.2.5.1, 14.2.5.2, 14.2.5.3, 14.2.5.4 and figures 14.2.1.18, 14.2.1.19, 14.2.1.20, 14.2.1.21, 14.2.1.22, 14.2.1.23, and 14.2.1.24 are added for Part A.
 
Tables 14.2.6.3, 14.2.6.4, 14.2.6.5, 14.2.6.6 and figures 14.2.1.19, 14.2.1.20, 14.2.1.21, 14.2.1.22, 14.2.1.23, 14.2.1.24 and 14.2.1.25 are added for Part BII.

V2.1	PPD	
Section 20.4: Additional information of 'The number (n) and percentage (%) at baseline, Cycle 3 Day 28 and Cycle 6 Day 28 showed a Spleen Volume reduction \geq 35%' is added.
 
MedDRA dictionary (version 19.0) changed to MedDRA dictionary (version 20.1) and WHO-DRL Drug Dictionary (Version 01MAR2016) changed to WHO-DRL Drug Dictionary (Version 01SEP2017)
 
Section 15.1: '+1' removed from the Per visit" Compliance calculation formula.
 
Added the text 'Also for the last cycle compliance calculation this formula will be used as the last dose of study drug date considering from disposition page.'

V2.2 (Addendum)	PPD	
1. Analysis performed for mathematical application of ELN response criteria (not agreed by the medical site team) and following tables are added.
 
Part A: 14.2.1.1.1, 14.2.1.4.1, 14.2.1.7.1, 14.2.1.8.1, 14.2.1.9.1, 14.2.1.10.1
 
Part B: 14.2.1.1.1, 14.2.1.3.1, 14.2.2.1.1, 14.2.2.2.1, 14.2.2.3.1, 14.2.2.4.1, 14.2.9.1, 14.2.9.3, 14.2.2.7, 14.2.2.8.
 
2. The following tables/Figures are

Document: PPD

Author: PPD

Version Number: V2.2
 Version Date: 21 March 2018

Template No: CS_TP_BS016 – Revision 3
 Effective Date: 01May2012

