5.3.1. PROTOCOL DEVIATIONS

Protocol deviations to be reviewed will include, but will not be limited to, patients who:

- Did not meet inclusion/exclusion criteria or eligibility not adequately verified.
- Received disallowed concomitant medications pre- and/or post-treatment.
- Developed withdrawal criteria but were not withdrawn.

According to Quintiles SOPs the PDs are classified as Minor, Major and Critical. Starting from 1st March 2016, the categorization changed into Minor, Important (for Major) and Priority (for Critical).

In order to comply with the Protocol requirements, the categorization of 'Critical', 'Important' and 'Priority' will fall into the 'Major' one.

A. Major protocol deviations to be reviewed will include, but will not be limited to, the following groups:

1. Entry criteria:

- Any "no" response to inclusion criteria and/or any "yes" response to exclusion criteria and patient was subsequently enrolled.

NOTE: only in case of previous written Sponsor authorization this type of deviation can be considered

Document: PPD

Author: PPD

Version Number:

V2.2

Version Date:

21 March 2018

Template No: CS_TP_BS016 – Revision 3

Reference: CS_WI_BS005

Effective Date: 01May2012

Copyright © 2012 Quintiles Transnational Corp. All rights reserved.

The contents of this document are confidential and proprietary to Quintiles Transnational Corp. Unauthorized use, disclosure or reproduction is strictly prohibited.

as 'Minor'.

2. Investigational Medicinal Product:

- Investigational Product dosing error: in case the patient takes a dose of IP that is different from the assigned dose (example: dose level, DL0, DL1, DL6 or MTD as defined at the end of study Part A).
- Enrolled out of DL - NOTE: only in the case of previous written Sponsor authorization to have the patient enrolled on cohort DL0 this is not considered as a protocol deviation.
- Part A (between C2D1 and C6D28) and Part B: Non-compliant with IMP usage (under 80%). According to the protocol "A patient will be considered sufficiently compliant with Givinstat treatment if he/she has taken at least 80% of the prescribed dose over the total duration of study drug dosing".

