16.10. ADVERSE EVENTS

All AEs either observed by the Investigator, or reported by the patient spontaneously or in a response to a direct question are evaluated by the Investigator and are recorded on the AE section of the electronic CRF.

If the patient discontinues for any reason (including discontinuation for pregnancy), with drug related adverse event ongoing at Study end, he/she will be followed until resolution or stabilization of the event or until it will be reasonable to consider the event not drug related any more or until the start of a new treatment, whichever occurs first.

In case of multiple reasons (e.g. patient withdraws the consent for toxicity), "adverse event" is indicated as the primary reason whenever applicable. All relevant information related to the reason for treatment discontinuation including contributory factors are included on the electronic CRF.

A complete end of Study visit must be performed by 7 days after the last drug intake for any patient permanently discontinuing Study treatment. All drug-related AEs that are still ongoing beyond the last scheduled visit, are followed at subsequent follow-up visits until recovery. If a patient does not return for a scheduled visit, every effort will be made to contact the patient. In any circumstance every effort will be made to complete and report the observations as thoroughly as possible. All relevant information related to the reason for treatment discontinuation including contributory factors are included on the electronic CRF.

For AEs definitions, coding and reporting procedures see [paragraph 5](#) of the Study protocol.

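### SAP section 15.1 gives two unreconciled end dates for the compliance denominator of patients who stop treatment, and one of them counts days off drug

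*SAP*

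**What the plan says.** Section 15.1 gives a per-visit and an overall compliance formula, both based on capsule counts. The per-visit denominator runs from *Date of Visit (n)* to *Date of Visit (n+1)*. The overall denominator runs from dispensing at Cycle 1 to *Date of Cycle(n)*, plus one day. Two consecutive sentences then adjust the end of treatment:

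- For the last cycle, "this formula will be used as the last dose of study drug date considering from disposition page".
- For patients who permanently stop, *Date of visit (n)* "will be replaced by the date of study withdrawal".

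Section 15 defines per-interval compliance against the capsules that should have been taken "for the duration of actual treatment exposure for that interval". Sections 15 and 15.1 set the sufficiency threshold at "at least 80% of the prescribed dose over the total duration of study drug dosing".

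The result feeds the analysis sets. Section 5.3.1 lists compliance under 80% as a Major deviation, for Part B and for Part A between C2D1 and C6D28. Section 5.3 admits to the Per Protocol (PP) set only ITT patients with at least 14 uninterrupted daily doses and no major deviation. Under sections 5.2 and 17.2, a patient who leaves for a drug-related TEAE before the efficacy measurement stays in ITT as a non-responder.

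**The concern.** For a patient who permanently stops, the last cycle is exactly where both sentences apply, and they can give different dates. The SAP sets no order of precedence, so two programmers could both follow the text and report different compliance for the same patient.

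Only the last-dose date fits the SAP's own definitions. Days between the last capsule and withdrawal are not treatment exposure, and no capsule is due on them. Counting them lowers the compliance of an adherent patient for a reason unrelated to adherence.

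The term named for replacement is a second problem. In the per-visit formula, *Date of Visit (n)* opens the interval. Substituting the withdrawal date there leaves a denominator running from withdrawal to the next visit, which does not measure time on drug.

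At stake are the reported compliance tables and the make-up of the PP set. Section 5.3 uses that set to test the robustness of the efficacy result, and section 17.2 reports the Part B primary endpoint on it. Patients lost in this way after a drug-related TEAE drop-out would be non-responders.

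**Working it through.** The SAP states no computed compliance figure, so there is none to reproduce. The check applies its formulas to an adherent patient.

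**Inputs**

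- d: number of dosed days, Day 1 to Day d. PP needs d of at least 14 (section 5.3).
- g: days from last dose to withdrawal. The SAP does not give it, so it is an assumption. The nearest stated figure is in section 16.10: "A complete end of Study visit must be performed by 7 days after the last drug intake". I use 7 days as the reference and show other values.
- Threshold: under 80% (sections 5.3.1 and 15.1).
- A constant number of capsules per day, with dispensing and first dose on Day 1.

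**Overall formula, withdrawal date as the end**

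Days in the denominator = (d + g) − 1 + 1 = d + g. Capsules cancel, so compliance = 100 × d/(d + g).

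It is under 80% when d < 0.8(d + g), that is, when g > d/4.

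| Dosed days d | g = 0 | g = 3 | g = 7 | g = 14 | Smallest whole-day g giving under 80% |
|---|---|---|---|---|---|
| 14 | 100 | 82.4 | 66.7 | 50.0 | 4 |
| 21 | 100 | 87.5 | 75.0 | 60.0 | 6 |
| 27 | 100 | 90.0 | 79.4 | 65.9 | 7 |
| 28 | 100 | 90.3 | 80.0 (passes) | 66.7 | 8 |
| 42 | 100 | 93.3 | 85.7 | 75.0 | 11 |
| 56 | 100 | 94.9 | 88.9 | 80.0 (passes) | 15 |
| 84 | 100 | 96.6 | 92.3 | 85.7 | 22 |

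With g = 7 and the 14-dose minimum for PP, the affected stops are Days 14 to 27.

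**Imperfect adherence**

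At 90% true adherence and g = 7, compliance is 0.9d/(d + 7). This is under 0.8 when 0.1d < 5.6, so for d below 56. At d = 56 it is 50.4/63 = 80.0%, which passes.

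**Per-interval figure**

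If withdrawal is taken as the end of the last interval, a fully adherent patient with k dosed days in it scores k/(k + g). With g = 7: k = 7 gives 50.0%, k = 10 gives 10/17 = 58.8%, k = 21 gives 75.0%, k = 28 gives 80.0%. Earlier treatment does not enter, so a late stopper can also be classed as too low in that interval.

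**Last dose date as the end**

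Overall compliance is d/d = 100% for a fully adherent patient, whatever g is.

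**Route to the PP set**

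With g = 7 the affected stops on the overall formula, Days 14 to 27, fall in Cycle 1. For Part A, the deviation criterion starts at C2D1, so the consequence is for Part B. PP also requires ITT membership. A patient who stops this early without an efficacy measurement is in ITT only after a drug-related TEAE drop-out, as a non-responder.

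To show the direction with assumed counts: 17 responders of 28 is 60.7%. Losing two such non-responders gives 17/26 = 65.4%.

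**The case against.** A reader might infer that the plan simply uses withdrawal in place of the last dose. It does not: the preceding sentence, added in V2.1, already uses the last dose date for the last cycle, and the 80% rule is worded over the duration of dosing. The defect is an unresolved conflict between two rules.

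A reader might also infer that adherent early stoppers in general leave the PP set. The documents do not support that, for four reasons:

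- The SAP does not define the date of study withdrawal. The 7 days is an upper limit for a visit, not a documented withdrawal lag. Withdrawal could be dated on the day of the last dose, and then nothing changes.
- At 7 days, only fully adherent patients who stop on Days 14 to 27 are affected. For the PP set this means Part B and, without an efficacy measurement, drug-related TEAE drop-outs. That may be a few patients or none.
- Section 5.3.1 words its criterion over the total duration of dosing, not by the section 15.1 formula, and has potential deviations reviewed case by case before lock. Exclusion is not automatic.
- The low per-interval figures bear on the compliance tables and not on the overall 80% rule.

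Nor does the literal label always give a zero or negative interval. If the next visit follows withdrawal, the interval is positive, though still not time on drug. The (n) also matches the end term of the overall formula, so a labelling slip is plausible.

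All of this limits the size of the problem. It does not settle which date applies, and a case-by-case review would start from a figure that may be wrong.

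**Conclusion.** The point holds as a contradiction in section 15.1, with a limited consequence. One of the two rules conflicts with the SAP's own definition of compliance, and the term it replaces is misnamed for the per-visit formula.

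If the withdrawal rule is followed as the end of the denominator, overall compliance of a fully adherent stopper is understated by the factor d/(d + g) and falls under 80% only when g exceeds d/4. How often that happens depends on a gap that the SAP does not state. Any wrongful PP exclusion of a Part B drug-related TEAE drop-out would remove a non-responder and raise the PP response rate. Per-interval compliance of stoppers is understated whenever there is a gap. The ITT analysis does not use compliance and is unaffected.

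**What to change.** In section 15.1:

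1. Delete the withdrawal-date sentence.
2. State that, for any patient who permanently stops, the last interval and the overall denominator both end on the date of last study drug intake (RFENDTN, section 14).
3. Name the term replaced: *Date of Visit (n+1)* in the per-visit formula and *Date of Cycle(n)* in the overall formula.

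The cost is SAP wording and the matching programming. Section 14 already takes RFENDTN from the Patient Disposition form, so no new data are needed.
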